6. Genotype 1a patients will be required to have historical resistance-associated variants (RAV) testing or done at screening if not previously performed
7. Patients are candidates for treatment of HCV with oral Direct-Acting Agents (DAA)
8. understand the study procedures, alternative treatments available, risks involved with the study, and voluntarily agrees to participate by giving written informed consent
9. Abstain from sexual intercourse will taking study medications and for 14 days after the last dose of study medications

Patients will be excluded from the study if they fulfill any of the following criteria:

1. Patient not willing to sign written informed consent
2. Patients deemed not suitable for HCV treatment as deemed by the treating physician at the liver center
3. Patients with decompensated liver cirrhosis, defined as follows:
 - a. Liver biopsy within the last year showing Scheuer Stage 4 or transient elastography (Fibroscan®) in the last year with a reading of >12.5 kPa;

AND

- b. Any clinical sign of hepatic decompensation such as ascites (fluid in the abdomen), jaundice (yellowing of eyes and skin), esophageal varices with bleeding (enlarged veins of the esophagus seen on endoscopy) or hepatic encephalopathy (tremors, confusion, sleepiness)
4. Co-Infection with the Hepatitis B virus
5. Any liver disease of non-HCV etiology such as Hemochromatosis, Wilson's Disease, Alcoholic liver disease or Non-Alcoholic Steato-Hepatitis (NASH)
6. Hepatocellular carcinoma or any other malignancy
7. Untreated psychiatric conditions such as major depression, schizophrenia, bipolar disorder which in the opinion of the Principal Investigator will not interfere with protocol visit and/or procedures
8. Current and untreated substance abuse (cocaine, opiates, alcohol, marijuana, other recreational drugs, controlled substances)
9. Patient is pregnant or breastfeeding.
10. Patients unwilling to use cellular phones
11. Patients unwilling to follow specific instructions for medication intake
12. Patient has any of the following conditions:
 - Organ transplants (including hematopoietic stem cell transplants) other than cornea and hair.
 - Poor venous access that precludes routine peripheral blood sampling required for this trial.
 - History of gastric surgery (e.g., stapling, bypass) or subject with a history of malabsorption disorders (e.g., celiac sprue disease).

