 - History of a medical/surgical condition that resulted in hospitalization within the 3 months prior to enrollment, other than for minor elective procedures
 - Medical/surgical conditions that may result in a need for hospitalization during the period of the study
 - Any medical condition requiring, or likely to require, chronic systemic administration of corticosteroids, TNF antagonists, or other immunosuppressant drugs during the course of the trial
13. has exclusionary laboratory values as listed below:
 - Noncirrhotic/Cirrhotic Subjects**
 - Creatinine clearance < 50 mL/min
 - Hemoglobin <9.5 g/dL for both male and female subjects
 - Platelets <50 x 10³/μL
 - serum albumin < 3.0 g/dL
 - INR >1.7, unless subject has a stable INR on an anticoagulant regimen.
 - HbA1c >10%
 - ALT >10XULN
 - AST >10XULN

14. is or has an immediate family member (e.g., spouse, parent/legal guardian, sibling or child) who is investigational site or sponsor staff directly involved with this trial.

15. agree to the following:

- The subject is a female who is not of reproductive potential, defined as a female who either: (1) is postmenopausal (defined as at least 12 months with no menses in women \geq 45 years of age); (2) has had a hysterectomy and/or bilateral oophorectomy, bilateral salpingectomy, or bilateral tubal ligation/occlusion at least 6 weeks prior to screening; OR (3) has a congenital or acquired condition that prevents childbearing.

- The subject is a female who is of reproductive potential and agrees to avoid becoming pregnant while receiving study drug and for 14 days after the last dose of study drug by complying with one of the following: (1) practice abstinence† from heterosexual activity OR (2) use (or have her partner use) acceptable contraception during heterosexual activity. Acceptable methods of contraception are‡:

Single method (one of the following is acceptable):

- intrauterine device (IUD)
- vasectomy of a female subject's male partner
- contraceptive rod implanted into the skin

Combination method (requires use of two of the following):

- diaphragm with spermicide (cannot be used in conjunction with cervical cap/spermicide)
- cervical cap with spermicide (nulliparous women only)
- contraceptive sponge (nulliparous women only)
- male condom or female condom (cannot be used together)

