For Group 1, the cap of the study drug bottle will be replaced with the Portal724- MEMS Smart Cap. A cellular phone per patient will also be provided. The Smart Cap in this study is to be outfitted to send messages to a website to which only the investigators and the research assistants have access to monitor medication adherence. Patients are to be instructed to open their study drug bottles in areas where there is at least 1 cellular signal bar. Patients will also be instructed to take their medications at specific agreed upon times. Once the agreed upon times are set, these will be programmed into the Smart Caps through a software program. The Smart Caps are encoded to not only record each pill bottle opening, it also will transmit an alert to the aforementioned website when the bottle is not opened within 2 hours of the agreed upon time. This alert is then seen by the Investigator or the Research assistant through a computer or their smartphone. The Investigator or Research Assistant in turn calls the cellular phone provided to the patient to remind the participant to take their medication, thus providing real-time feedback. Group 2 (the control group) will be provided MEMS Smart Cap to record study drug bottle opening, but without real-time feedback and will be managed as per the standard of care at the Liver Center SMMC.

Patients from both groups will be seen in the Liver Center at Day 1, weeks 2, 4, 8 and 12 from start of treatment. They will be seen by Liver Center Physician together with the Investigator and Research Assistant at each visit. They will also be counseled about the importance of medication adherence at every visit by the Liver Center physician. At each visit, patients are instructed to bring with them all of their anti-HCV study drug bottles for pill counting to be done by the Investigator and Research Assistant. Patients in ARM 1 will also get feedback about their medication compliance using the Smart Caps per visit.

After completion of treatment as determined by the Liver Center Physician, patients from both groups are to follow-up at week 4 and week 12 post-treatment. At that time, an HCV RNA PCR viral load will be obtained to determine if patient has an undetectable viral load, or Sustained Virologic Response (SVR). SVR is the marker for a functional cure of HCV, or treatment success. Non-SVR would mean treatment failure.

Study Procedures	Pre-Treatment						Treatment Assessments		Post Tx	Post tx

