Fourteen patients have discontinued the MK-5172 therapy early due to a side effect. In some cases the patients discontinued only MK-5172 and in other cases the patients discontinued all therapy. The side effects that led to the study drug being stopped included decrease in the blood cells that carry oxygen, increased bilirubin, low blood pressure, weakness, headache, flu-like illness, irritability, shortness of breath, dehydration, fear/nightmares, anxiety/depression, increased levels of transaminases, nausea, reactivation of chronic pancreatitis (inflammation of an abdominal gland) and myositis (inflammation of the muscles). Not all of these side effects were considered to be related to MK-5172.

Ribavirin

COMMON ADVERSE EVENTS

The most common side effects when taking ribavirin combined with pegylated interferon are flu-like symptoms consisting of:

- Body aches and pains
- Fever
- Chills
- Headache
- Overall feeling of sickness
- Rash

Other common side effects are: anxiety, mood changes, depression and irritability.

The most serious side effect seen with RBV is anemia (a decrease in the number of red blood cells in your body that carry oxygen). Which may cause tiredness and lack of energy. Other side effects may occur which are not listed here or were not seen before.

Ribavirin can cause severe damage and even death of an unborn child or fetus. **Extreme care should be taken to prevent pregnancy while you are taking RBV and afterwards. Patients will be required to abstain from sexual course while taking ribavirin and for 6 months after the last dose of ribavirin**

DILI

In the event of a discontinuation of grazoprevir/elbasvir for suspected ***DILI***, other clinically significant liver chemistry elevations (defined under "Liver Chemistry Stopping and Follow up Criteria", below), severe skin reaction or hypersensitivity reaction, subjects should not restart grazoprevir/elbasvir due to the risk of a recurrent reaction; such subjects should be withdrawn from study and seek/be reviewed for alternative HCV therapy.

Allergic Reaction

Subjects may continue study medication for Grade I or 2 allergic reactions at the discretion of the Investigator. The subject should be advised to contact the Investigator immediately if there is any worsening of symptoms or if further systemic signs or symptoms develop. Antihistamines, topical corticosteroids, or antipruritic agents may be prescribed.

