Subjects with Grade 2/3 allergic reactions that are considered to be possibly or probably related to the study medication should permanently discontinue the regimen and the subject should be withdrawn from the study. Subjects should be treated as clinically appropriate and followed until resolution of the AE.

Adverse events**Adverse Experience (Event)**

An adverse experience means any unfavorable and unintended change in the structure, function, or chemistry of the body temporally associated with any use of the Merck product whether or not considered related to the use of the product. Any worsening (i.e., any clinically significant adverse change in frequency and/or intensity) of a preexisting condition which is temporally associated with the use of the product, is also an adverse experience.

Serious Adverse Experience

A serious adverse experience (SAE) is any adverse experience occurring at any dose that:

- Results in death
- Is life threatening (places the subject/patient, in the view of the investigator, at immediate risk of death from the experience as it occurred)
- Results in a persistent or significant disability/incapacity
- Results in or prolongs an existing inpatient hospitalization
- Is a congenital anomaly/birth defect
- Other important medical events that may not result in death, not be life threatening, or not require hospitalization may be considered a serious adverse experience when, based upon appropriate medical judgment, the event may jeopardize the subject/patient and may require medical or surgical intervention to prevent one of the outcomes listed above. Examples of such medical events include allergic bronchospasm requiring intensive treatment in an emergency room or at home, blood dyscrasias or convulsions that did not require hospitalization, or development of drug dependency or drug abuse.
- Is an overdose (whether accidental or intentional)
- Cancer (that is not the condition under the study)*

*If disease progression is noted during a protocol-specified reevaluation of the status of a patient's cancer and the progression is manifested solely by results of tumor markers and/or radiologic imaging, that occurrence of progressive disease will NOT be recorded as an adverse experience.

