All Serious Adverse Experiences, regardless of causal relationship to the investigational product, must be forwarded to **Merck Worldwide Product Safety** via fax (**[contact]**) within 2 working days of the investigator becoming aware of the event and no later than 3 calendar days.

Minimum protocol required language (ie, site has most of the language noted above):

Merck (Attn: Worldwide Product Safety; [contact]) will be provided with copies of all serious adverse experiences regardless of causality to use of a Merck product within two working days. Additionally, any pregnancy occurring in association with use of a Merck Product will be reported (Attn: Worldwide Product Safety; [contact]).

A copy of all 15 Day Reports and Annual Progress Reports is submitted as required by FDA, European Union (EU), Pharmaceutical and Medical Devices agency (PMDA) or other local regulators by the investigator. This submission will be cross referenced according to local regulations to the Merck Investigational Compound Number (IND, CSA, etc.) at the time of submission. Additionally, a copy of these reports will be submitted to Merck (Attn: Worldwide Product Safety; [contact]) at the time of submission

Ethics

Institutional review board

Before initiation of the study, the Investigator(s) will submit the study protocol, sample Informed Consent Form, and any other documents to the IRB for approval. The study will not commence until there is full IRB approval. All IRB regulatory material will be properly filed and available for review by the proper organizations.

Confidentiality

Patients will be assigned research participant numbers which will be used by the investigators to identify them. This number plus other data that will be collected from the participants will be kept in password-protected file, only accessible to the Investigator and Research Assistant. Data transmitted by the Portal724- MEMS Smart Cap will only be identified through the research participant number.

Statistical Analysis

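### Scheduled contact ends 12 weeks after treatment while the ribavirin precaution runs 6 months, so nothing scheduled would detect a pregnancy in about the last 14 of those 26 weeks

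*Combined protocol and SAP*

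**What the plan says.** Three of the six groups under Treatment Arms receive ribavirin, always together with elbasvir/grazoprevir and for 16 weeks.

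- **Risk and precaution** (Toxicity management, Ribavirin): "Ribavirin can cause severe damage and even death of an unborn child or fetus". The rule that follows is "Patients will be required to abstain from sexual course while taking ribavirin and for 6 months after the last dose of ribavirin".
- **Follow-up** (Enrollment): "patients from both groups are to follow-up at week 4 and week 12 post-treatment". In the schedule table the last adverse event mark is at post-treatment week 12, and there is no later column. No row at any visit covers pregnancy, by test or by question.
- **Reporting** (Adverse events): "any pregnancy occurring in association with use of a Merck Product will be reported". Serious events go to the manufacturer "within 2 working days of the investigator becoming aware of the event and no later than 3 calendar days". The list of serious criteria includes "Is a congenital anomaly/birth defect". No end date is attached to either duty.
- **Eligibility** (Study Patient Population): inclusion criterion 9 reads "Abstain from sexual intercourse will taking study medications and for 14 days after the last dose of study medications". Item 15 of the exclusion list, on women of reproductive potential, reads "agrees to avoid becoming pregnant while receiving study drug and for 14 days after the last dose of study drug".

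**The concern.** The plan takes the fetal risk seriously enough to attach a 6-month precaution, yet its last planned contact comes less than halfway through that time. A site following the schedule exactly has no occasion after week 12 to ask about pregnancy. A pregnancy in a participant, or in the partner of a male participant, would reach the safety record only if someone volunteered it. At stake is the completeness of the safety data on exposed pregnancies, and the chance to follow them. The adherence and SVR comparisons are not affected.

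**Working it through.** The plan states no figure of its own for this gap, so there is none to reproduce. The check is date arithmetic plus a comparison of passages.

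**Inputs.** Precaution after the last ribavirin dose: 6 months (Ribavirin text), taken as 182.625 days, about 26 weeks. Last scheduled contact: post-treatment week 12 (Enrollment; schedule table), which is 12 × 7 = 84 days.

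**Gap if ribavirin is taken to the end of treatment.** Days without contact = 182.625 − 84 = 98.6, or 14.1 weeks. Share = 98.6 / 182.625 = 54.0%.

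**Sensitivity to the length of 6 months.**
- 180 days: (180 − 84) / 180 = 53.3%
- 184 days: (184 − 84) / 184 = 54.3%
- 168 days (a month read as 4 weeks): (168 − 84) / 168 = 50.0%

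**Sensitivity to stopping ribavirin early.** If ribavirin stops k weeks before the rest of the regimen, the share is (182.625 − 84 − 7k) / 182.625.
- k = 1: 50.2%
- k = 2: 46.3%
- k = 4: 38.7%
- k = 8: 23.3%

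**If the 14-day text governs.** 84 − 14 = 70, so the week-12 visit falls 70 days after the period ends and there is no gap. The finding therefore depends on how the 14-day and 6-month passages are reconciled. They might be meant as separate rules for separate drugs, but criterion 9 speaks of study medications without setting ribavirin apart.

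**Do the reporting duties fill the gap?** The serious event clock starts when the investigator becomes aware. The pregnancy line likewise can act only on a pregnancy that is known. After week 12 no visit, call or test creates that knowledge. The pregnancy line names a Merck product and is silent on partners, although men are eligible and the 6-month rule is not limited to women. It does not say whether a conception months after ribavirin counts as associated with use. The birth-defect criterion has the same limit: the underlying adverse event definition is tied in time to use of the Merck product, and a birth after a conception in the gap would come well after contact had ended.

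**How many patients.** The documents give no ribavirin share of the 40. Assumed shares of 20% and 50% would give 0.20 × 40 = 8 and 0.50 × 40 = 20, but neither share comes from the plan. The number could be below 8: two of the three ribavirin groups are treatment-experienced only, while inclusion criterion 2 requires treatment-naïve status. Not every recipient is at risk of a pregnancy, either.

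**The case against.** The strongest reply is that the plan already requires pregnancies and serious events to be reported, without an end date, and counts a birth defect as serious. A reader might infer from the schedule that pregnancies after week 12 go uncollected or have no route to be reported. The documents do not support that: a pregnancy the site learns of can still be reported. What is missing is a scheduled prompt.

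A reader might also infer that the Merck product wording shuts ribavirin recipients out. It does not clearly do so, since each of them also takes elbasvir/grazoprevir, and the documents do not say who makes the ribavirin. The wording is unclear, not an exclusion.

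Three further points stand. The 6 months is a rule of conduct, and nothing in the plan says safety collection must match it; aligning the two is a design judgement. The documents do not rank fetal harm as the worst ribavirin risk; they call anemia the most serious side effect seen. And the 46% of the period before week 12 is general adverse event contact, not pregnancy monitoring, because the schedule has no pregnancy item there either.

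Finally, the consent pages were not available for this review, so an instruction there telling patients to report a pregnancy cannot be ruled out. Such an instruction would soften the gap but would still leave detection to the patient.

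**Conclusion.** The point holds as a gap in scheduled detection for ribavirin recipients and their partners. Its size is about 14 of 26 weeks (54%), assuming that the 6-month period applies and that ribavirin is taken to the end of treatment. It disappears if the reconciled period ends by post-treatment week 12. The number of patients concerned cannot be derived from the documents and may be small; no expected number of pregnancies can be given. The open-ended reporting duties limit the consequence but do not remove it, because they wait on awareness that nothing scheduled after week 12 provides. This is a cheap safety improvement and does not threaten the trial's comparisons.

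**What to change.** 1. Reconcile the 14-day text (inclusion criterion 9 and item 15 of the exclusion list) with the 6-month text under Ribavirin, stating which drug and which participants each period applies to. The choice of period is clinical and none is proposed here.
2. For ribavirin recipients, align pregnancy collection, for patient and partner, with the reconciled period and show it as a row in the schedule table.
3. If that period runs past post-treatment week 12, add one telephone contact at its end as a new schedule column. With 6 months this falls about 14 weeks after the week-12 visit.
4. Reword the pregnancy reporting line under Adverse events to cover exposure to any study drug, including ribavirin, and pregnancies in partners.

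The cost is protocol wording, one schedule row and column, and one call per ribavirin recipient. The downside is that those patients close later. The adherence and SVR analyses need not wait for the calls.

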	Screening (Day 35 to -1)	Baseline (Day 0)	WK2	Wk4	Wk8	Wk12/16	Wk 4	Wk 12		
	Informed Consent w/ Med Hist inc HIV status	x								
Complete PE inc. Vital Signs	x	x								
Symptom Directed PE inc. Vital Signs			x	X	X	X	x	x		
12-lead ECG	x									
Chemistry(Comprehensive Metabolic Panel)	x	x	x	x	x	x	x	x		
Hematology	x	x	x	x	x	x	x	x		
Virology(HCV)	x	x	x	x	x	x	x	x		
AEs		X	X	X	X	X	X	X		
Con Meds	X	X	X	X	X	X	X			
MEMS download		x	x	x	x	x				

Data Collection

At each visit, the following data are to be collected: HCV RNA PCR viral load, CBC, complete metabolic profile, number of pills missed. For both groups, Number of times pill bottles were opened will also be collected.

Primary outcome measures:

Primary endpoint in the study is the effect of the use of Portal724-MEMS Service on medication adherence, defined as compliance to regimen $\geq 95\%$ of the time.

Secondary outcome measures:

The secondary endpoints for the study include the effect of the use of Portal724-MEMS Service on SVR, factors that affect medication adherence, such as race/ethnicity, age, educational attainment. Additionally, the feasibility of using MEMS adherence technology in an inner city urban population will be evaluated.

Statistical Analysis

This is a pilot study intended to generate initial data on the use of MEMS technology in an inner city population to assess its feasibility and impact on treatment outcomes in HCV infected patients. Wilcoxon signed-rank test will be used to compare Groups 1 and 2 in terms of achieving adherence 95%.

SVR between the groups will also be analyzed in the same manner. A descriptive analysis will be done outlining patients' profiles. Fischer's exact test will be used to compare baseline characteristics between Groups 1 and 2. Alpha level for all statistical analysis will be set at 0.05.

Toxicity management

Grazoprevir/elbasvir

The following side effects have been reported when MK-5172 in doses ranging from 25 mg to 800 mg or placebo (a tablet that looks the same as the MK-5172 but has no active ingredient) was given for up to 12 continuous weeks to 389 HCV-infected men and women at the same time as other drugs commonly given to HCV patients (pegylated interferon and ribavirin). These side effects were considered to be related to the treatment.

- Decrease in the blood cells that carry oxygen
- Decrease in blood cells that fight infection
- Stomach pain
- Diarrhea
- Upset stomach
- Dry mouth
- Nausea
- Vomiting
- Weakness
- Chills
- Fatigue

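### Patients stopped for toxicity leave the study with no scheduled SVR sample, early quitters may have none, and no rule says how either group counts in the SVR comparison

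*Combined protocol and SAP*

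**What the plan says.** Four parts of the combined protocol and SAP bear on this.

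- **Timing of SVR (Enrollment, follow-up paragraph).** "After completion of treatment as determined by the Liver Center Physician, patients from both groups are to follow-up at week 4 and week 12" post-treatment. The next sentence says "At that time, an HCV RNA PCR viral load will be obtained to determine if patient has an undetectable viral load", which is equated with SVR. It then says "Non-SVR would mean treatment failure". Two visits are named, and the text does not say which one decides SVR.
- **Withdrawal for liver, severe skin or hypersensitivity reasons (Toxicity management, DILI).** "such subjects should be withdrawn from study and seek/be reviewed for alternative HCV therapy".
- **Withdrawal for allergic reactions (Toxicity management, Allergic Reaction).** Patients with possibly or probably related Grade 2/3 reactions "should permanently discontinue the regimen and the subject should be withdrawn from the study". The only follow-up named for them is "Subjects should be treated as clinically appropriate and followed until resolution of the AE".
- **Use of SVR.** Under Secondary outcome measures: "The secondary endpoints for the study include the effect of the use of Portal724-MEMS Service on SVR". Both Statistical Analysis sections compare SVR between Groups 1 and 2 by the same test as adherence. Neither defines an analysis population or a rule for a missing SVR.

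The Study Procedures table has no early-termination visit.

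**The concern.** An SVR comparison that keeps the benefit of randomisation needs an outcome for every randomised patient. Here the withdrawal rules end study participation as well as drug intake, and the sampling rule starts from completing treatment. A site that follows both has no scheduled post-treatment HCV RNA for a toxicity-stopped patient. It may have none for a patient who simply quits.

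A sample not drawn at post-treatment week 12 cannot be recovered at analysis. A withdrawn patient who is later treated with something else may become undetectable for reasons unrelated to the study regimen, and the plan does not say how that counts.

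What is at stake is the SVR level in each arm and, if stopping differs between arms, the SVR difference. The intervention is meant to change how much treatment patients take, so an analysis restricted to those who completed would condition on something the intervention may affect.

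**Working it through.** The plan gives no SVR rate, stop rate or power for its 40 patients, so there is no stated figure to reproduce. The check shows what dropping stopped patients would do.

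**Inputs**

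- 40 patients, 20 per arm (Methods). One patient is 1/20 = 5 percentage points.
- SVR in completers, p_c: 90% or 95%. This is an assumption, guided by the Introduction's cure rates above 90% for other interferon-free combinations.
- SVR in stopped patients, p_s: 0% to 32%. This is an assumption. The Introduction gives 8–32% below 80% adherence, on older regimens. No SVR rate after a toxicity stop is given.
- Stop proportion, w: an assumption. Toxicity management mentions 14 side-effect discontinuations without a denominator. Separately it mentions 389 people given MK-5172 or placebo on a peginterferon/ribavirin background. Pairing the two gives 14/389 = 3.6%, a rough scale only.

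**Step 1: how many stops.** At 3.6%, the expected number is 40 × 0.036 = 1.4 patients. By the binomial, P(at least 1 of 40) = 77% and P(at least 3 of 40) = 17%. For one arm of 20, P(at least 3) is about 3%. Voluntary quitting would add to these counts.

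**Step 2: effect on the SVR level.** SVR in all randomised = (1 − w) × p_c + w × p_s. Dropping stopped patients reports p_c instead, so the overstatement is w × (p_c − p_s).

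| w | Smallest (p_c 90%, p_s 32%) | Largest (p_c 95%, p_s 0%) |
|---|---|---|
| 3.6% | 0.036 × 0.58 = 2.1 points | 0.036 × 0.95 = 3.4 points |
| 5% | 0.05 × 0.58 = 2.9 | 0.05 × 0.95 = 4.8 |
| 10% | 0.10 × 0.58 = 5.8 | 0.10 × 0.95 = 9.5 |
| 15% | 0.15 × 0.58 = 8.7 | 0.15 × 0.95 = 14.3 |

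**Step 3: effect on the difference (invented counts).**

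- *Equal stopping, one per arm.* Patients with data: 18/19 vs 18/19 (94.7% each). All randomised, missing counted as failure: 18/20 vs 18/20 (90% each). The level falls by about 5 points and the difference stays 0.
- *Unequal stopping, none vs three.* Patients with data: 19/20 (95%) vs 16/17 (94.1%), a difference of 0.9 points. All randomised, missing counted as failure: 19/20 (95%) vs 16/20 (80%), a difference of 15 points (Fisher p = 0.34).

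The second case recovers the true difference only if the three unsampled patients really did fail. That is a reason to collect the samples as well as to impute.

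**The case against.** Several points against a stronger claim are sound.

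- A reader might infer that the plan prescribes a completers-only SVR analysis. It does not. No sentence excludes withdrawn patients, the comparison is of Groups 1 and 2, and the follow-up sentence refers to patients from both groups. Completion as determined by the physician can also be read as any end of treatment. That reading rescues patients who quit, but not those removed from the study.
- A reader might infer that the toxicity withdrawals bias the comparison against feedback. The documents do not support that. The same withdrawal rules and study treatments apply in both arms, and nothing suggests reminder calls change the rate of liver or allergic reactions. Nor is a mandated stop the same as non-adherence: the Introduction's remark on relapse concerns patients who did not comply.
- A reader might take 14 of 389 as a reported rate. The documents do not pair the figures, the 389 includes placebo recipients, and some listed reasons for stopping, such as headache or irritability, would not trigger these withdrawal rules. Withdrawals under the rules could be fewer than 1 to 2 of 40.
- The DILI paragraph points to Liver Chemistry Stopping and Follow up Criteria that are not in the text available, so any follow-up they require cannot be checked.
- The stated objective is adherence, and SVR is secondary. At this size even 17/20 vs 19/20 gives Fisher p = 0.60, so no demonstrable SVR benefit is being hidden.

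These points limit the size of the problem and the confidence in it. They do not supply a sample or an outcome rule for the withdrawn patients.

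**Conclusion.** The gap is real and narrow. Patients withdrawn under the DILI and allergic-reaction paragraphs have no scheduled SVR sample, patients who quit early may have none, and no rule assigns either group an outcome. The surer consequence is an SVR rate that is too high in both arms: about 2 to 3 points at a 3.6% stop rate, rising to 9 to 14 points at 15%. This holds if stopped patients are dropped and reach 0–32% SVR against 90–95% in completers. All of those rates are assumptions.

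Bias in the between-arm difference needs unequal stopping. That is plausible for voluntary quitting, which feedback may affect, and has no support in the documents for toxicity stops.

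Because SVR is a secondary endpoint of a 40-patient pilot, the importance is modest. Confidence is medium, given the two readings of completion and the liver criteria that could not be checked.

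**What to change.** Decisions on stopping treatment remain with the protocol. The changes concern follow-up and counting.

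1. In the DILI and Allergic Reaction paragraphs, replace withdrawal from the study with discontinuation of study treatment and continued study follow-up.
2. In the follow-up paragraph, time the post-treatment week 4 and week 12 HCV RNA from the last dose taken, for every randomised patient and whatever the reason for stopping.
3. Define SVR on the week 12 sample, with week 4 supportive.
4. In Statistical Analysis, analyse SVR in all randomised patients by assigned arm. Count a missing week 12 sample, or other HCV therapy started before it, as non-SVR. Add an observed-data sensitivity analysis and report missing samples by arm and reason.
5. Reconcile the Allergic Reaction text, which lets Grade 2 reactions continue at the investigator's discretion and also requires related Grade 2/3 reactions to be discontinued and withdrawn. Until then it is unclear who is withdrawn. Check the cited liver chemistry criteria for consistency with item 1.

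The cost is wording, plus two already scheduled blood draws in a few patients. SVR rates will look slightly lower, and some cured patients with a missing sample will count as failures; the sensitivity analysis shows how much that matters. The change has to be made before patients stop, because the samples cannot be obtained afterwards.
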